15.3. Analysis Populations

Intent-to-Treat (ITT) Population: All randomized subjects who receive at least one dose of study medication and have at least 1 post-baseline result in any efficacy evaluation. The ITT population is the primary population for efficacy analyses, ie, unless otherwise specified, all efficacy analyses will be based on ITT population.

Per-Protocol (PP) Population: All ITT subjects who have no major protocol violations that may affect the interpretation of the primary efficacy endpoint.

The PP population will be used to assess robustness of the primary efficacy analysis. Major protocol violations and the PP population will be determined through a blinded data review meeting and identified prior to the database lock.

Subjects in the ITT and PP populations will be analyzed based on the treatment to which they are randomized.

Double-blind (DB) Safety Population: All randomized subjects who receive at least one dose of study medication.

The DB Safety population mainly will be used for the data analyses of the safety data collected through Week 12 or during the treatment period. Subjects will be analyzed based on the predominant treatment received, in the event that a subject receives a treatment other than the one to which he or she is randomized. The predominant treatment is defined as the treatment (ie, placebo, dasotraline 4 mg/day, or dasotraline 6 mg/day) to which the subject is exposed for the greatest duration during the treatment period. The predominant treatment will generally be the same as the randomized treatment group, unless the subject takes incorrect study medication during the entire study.

Withdrawal Safety Population: The Withdrawal safety population includes all randomized subjects who receive at least one dose of study medication, and either discontinue the study drug during the treatment period before the Week 12 visit or complete the 12-week treatment period but do not enter the extension study (Study SEP360-322), and have at least one assessment after the last dose of study medication for any safety or efficacy evaluation. The Withdrawal safety population mainly will be used to summarize the assessments collected in the withdrawal period.

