15.4.1.3. Key Secondary Efficacy Endpoints Analyses

The key secondary efficacy endpoints involved in the hypothesis testing of each dasotraline dose (4 mg/day and 6 mg/day) versus placebo include change from baseline at Week 12 in BE-CGI-S score and Y-BOCS-BE total score, and percent of subjects with a 4-week cessation from binge eating. If a subject is early terminated in the double-blind treatment period prior to collection of 28 days of diary data or the subject has missing diary data in the last 28 days prior to Week 12/EOT the subject will be counted as having no cessation.

Continuous key secondary variables (ie, change in BE-CGI-S score and Y-BOCS-BE total score) will be analyzed with an MMRM model similar to the primary efficacy analysis ([Section 15.4.1.2.1](#)) adjusted with the corresponding baseline. The LS mean treatment differences (each dasotraline group minus placebo) of change from baseline at Week 12, their 2-sided 95% CIs, and the associated p-values will be calculated based on the model.

Categorical secondary efficacy endpoints (ie, percent of subjects with a 4-week cessation from binge eating) will be analyzed using a logistic regression model with treatment, baseline binge days category (stratification factor; refer to [Section 7.2.1](#) for categories), and baseline number of binge days per week as covariate using a LOCF approach based on the ITT population. The odds ratios, their 2-sided 95% CIs, and the associated p-values for each dasotraline group over the placebo group will be derived from the model.

Additional supportive and sensitivity analyses may be conducted as needed for the key secondary endpoints to address early dropouts or potential deviation from the model assumption(s). To address early dropouts or potential deviation from the model assumption(s), supportive and sensitivity analyses similar to those described in [Section 15.4.1.2.3](#) may be

conducted as needed for the continuous key secondary endpoints. For the categorical key secondary endpoint, supportive and sensitivity analyses, such as a GLMM analysis with random effect(s) and a pattern-mixture model using placebo-based multiple imputations, may be conducted as appropriate. The details will be provided in the SAP.

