Based on the number of binge days and number of assessed days (defined in [Section 5.1.1.1](#)) at each visit, the number of binge eating days per week is calculated as

$(\text{total number of binge days}) \times 7 / (\text{total number of assessed days in the visit span});$

the number of binge eating episodes per week is calculated as

$(\text{total number of binge episodes}) \times 7 / (\text{total number of assessed days in the visit span}).$

5.1.1.3. Percent Reduction in the Number of Binge Eating Episodes from Baseline at Post-baseline Visits in DB Treatment Period

Percent change in the number of binge eating episodes from baseline at a post-baseline visit is calculated as:

321

(value at the post-baseline visit – value at baseline) / value at baseline for number of binge eating episodes per week;

Binary indicator for subjects who have $\geq 75\%$ reduction in the number of binge-eating episodes from baseline will be derived for each post-baseline visit in DB treatment period, respectively.

5.1.1.4. 4-Week Cessation

4-Week cessation from binge eating is defined as a 100% reduction for at least 28 consecutive days in the number of binge eating episodes at Week 12/EOT visit. If a subject is early terminated in the double-blind treatment period prior to collection of 28 days of diary data or the subject has missing diary data in the last 28 days prior to Week12/EOT, the subject will be counted as no cessation. See below for specific details about how to derive the variable:

Count the number of days from the first study dose date to the Week 12/EOT visit date,

- If a subject has less than 28 days, 4-week cessation flag will be set as ‘No’;
- If a subject has ≥ 28 days,
 - If missing diary entries exist during the last 28 days or no missing diary exist in the last 28 days but reduction $<100\%$, 4-week cessation flag will be set as ‘No’.
 - If no missing diary entries exist in the last 28 days and reduction =100%, 4-week cessation flag will be set as ‘Yes’.

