6.1.9 Analysis Populations

The Intent-to-Treat (ITT) Population: All randomized subjects who receive at least one dose of study medication and have at least 1 post-baseline result in any efficacy evaluation. The ITT population is the primary population for efficacy analyses, ie, unless otherwise specified, all efficacy analyses are based on ITT population.

The Per Protocol (PP) Population: All ITT subjects who have no major protocol violations that may affect the interpretation of the primary efficacy endpoint. The PP population will be used to assess robustness of the primary efficacy analysis. Major protocol violations and the PP population will be determined through a blinded data review meeting (BDRM) and identified prior to the database lock.

Subjects in the ITT and PP populations will be analyzed based on the treatment to which they are randomized.

The Double-blind (DB) Safety Population: All randomized subjects who receive at least one dose of study medication. The DB safety population mainly is used for the data analyses of the safety data collected through Week 12 or during the treatment period. Subjects are analyzed based on the actual treatment received; specifically, for subjects who are randomized to dasotraline 6 mg group and dosed with dasotraline 4 mg but never titrated to dasotraline 6 mg (ie, early terminated on or prior to Week 2 visit), the actual dose will be dasotraline 4 mg; otherwise, actual dose will be set as dasotraline 6 mg; In the event that a subject receives a treatment other than the one to which he/she is randomized or expected, the actual treatment is defined as the treatment to which the subject is exposed for the greatest duration during the treatment period. The actual treatment is generally the same as the randomized treatment group, unless the subject takes incorrect/unexpected dose during the entire study. Hereafter, DB safety population will be referred as safety population by default.

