7.2.1 Analysis Specifications

7.2.1.1 Level of Significance

Unless otherwise specified, all statistical tests will be interpreted at a 2-sided significance level of 5% and all confidence intervals (CIs) will be presented at a 2-sided confidence level of 95%.

The overall type I error rate for testing dasotraline 6 mg/day group versus placebo and dasotraline 4 mg/day group versus placebo will be strongly controlled at the 5% level across the primary endpoint and key secondary endpoints, which is detailed in [Section 6.2.5](#).

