The categorical key secondary efficacy endpoint of percent of subjects with a 4-week cessation from binge eating will be analyzed using a logistic regression model with treatment, baseline binge days category (stratification factor), and baseline number of binge days per week as covariate using a LOCF approach based on ITT population. The odds ratios, their 2-sided 95%

321

CI, and the associated p-values for each dasotraline group over the placebo group will be derived from the model.

As a supportive analysis, percent of subjects with a 4-week cessation from binge eating will be analyzed by an inverse probability weighting (IPW) model; See [Attachment 9.3.4](#) for details about IPW method ([6]). A sensitivity analysis per quasi-likelihood approach will be conducted by fitting same fixed terms as listed above with random-residual based on binary distribution with logit link, which will effectively lift the constraints of the model parameter. The above approach will be implemented using GLIMMIX procedure in SAS.

For above logistic regression model, two exploratory analyses will be performed using same predictor terms with an additional fixed term of planned or actual region group (pooled one when applicable), respectively, to evaluate the impact of mis-stratification of region on treatment effect and further corroborate key secondary efficacy results.

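### The 4-week cessation rule scores early leavers as failures, but the ITT set used to analyse it omits dosed subjects who have no post-baseline efficacy result

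*SAP*

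**What the plan says.** **Endpoint rule.** Protocol 15.4.1.3 and SAP 5.1.1.4 carry the same rule. It has two limbs. The first opens "If a subject is early terminated in the double-blind treatment period prior to collection of 28 days of diary data"; the second covers any gap in the diary over the final 28 days. Either way the outcome is failure, so incomplete data are resolved by definition and not by imputation.

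**Analysis set.** SAP 7.2.4.2 fits a logistic regression with treatment, the baseline binge-day stratum and "baseline number of binge days per week as covariate using a LOCF approach based on ITT population". SAP 6.1.9 limits ITT to "All randomized subjects who receive at least one dose of study medication and have at least 1 post-baseline result in any efficacy evaluation". Protocol 15.3 has the same condition: subjects must "have at least 1 post-baseline result in any efficacy evaluation".

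**Status.** Cessation is a key secondary endpoint. SAP 7.2.1.1 says that type I error is "strongly controlled at the 5% level across the primary endpoint and key secondary endpoints", with the procedure in SAP 6.2.5.

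**The concern.** The two provisions disagree about one kind of subject: someone who is randomized, takes at least one dose and then provides no efficacy result. The endpoint rule gives this person an outcome, while the analysis set removes the person before the outcome can count.

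For the MMRM endpoints the restriction costs nothing, because a subject with no post-baseline value adds nothing to the estimated change. SAP 6.1.11.3 in any case limits change-from-baseline analyses to subjects who have a post-baseline value. A binary endpoint with a failure rule is different. Every removed subject is a known failure, so each removal raises that arm's observed rate. Removal also depends on what happens after randomization, so the comparison is no longer between the groups as randomized. If the arms lose different shares, the odds ratio and p-value of an endpoint in the alpha-controlled sequence shift.

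**Working it through.** **Tracing one subject.** Randomization and dispensing are on Day -1 and the first dose is self-administered on Day 1 (Protocol 7.1). The diary is on paper, and the Investigator assesses the daily binge counts at visits (Protocol 11.3.1). The first post-baseline visit is Week 1; BE-CGI-S and Y-BOCS-BE follow at Week 2 (Protocol 11.8.2 and 11.8.3). A subject lost before any return visit is therefore likely to have no efficacy result.
- SAP 5.1.1.4: terminated before 28 diary days, so "the subject will be counted as no cessation". The step-by-step derivation there counts days up to the Week 12/EOT visit, which this subject lacks, but the lead sentence settles the case.
- SAP 6.1.9: not in ITT.
- SAP 7.2.4.2: not in the model. LOCF has nothing to carry forward. The supportive inverse-probability-weighted and quasi-likelihood analyses name no wider set, and ITT is the default for efficacy. Attachment 9.3.4, which holds the weighting detail, was not part of the text examined.

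**Figures in the plan.** There is none for cessation. The sample size concerns the primary endpoint only. It reproduces: 96 / (1 - 0.40) = 160 per arm, and conjunctive power with SD 1.75 and differences 0.9 and 0.8 is 85.4%, against the stated minimum of 85%. Only the 160 is used below.

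**Size under assumed rates.** Let p be the ITT cessation rate and q the share of dosed subjects whom the ITT rule removes. All removed subjects are failures, so the rate among all dosed subjects is p × (1 - q). Assume p = 35% on drug and 20% on placebo. The ITT analysis then shows a difference of 15.0 points and OR = (0.35/0.65) / (0.20/0.80) = 2.15.

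| Removed, drug / placebo | All-dosed rates | Difference | OR |
|---|---|---|---|
| 2% / 1% | 34.3% / 19.8% | 14.5 | 2.11 |
| 4% / 1% | 33.6% / 19.8% | 13.8 | 2.05 |
| 8% / 2% | 32.2% / 19.6% | 12.6 | 1.95 |
| 8% / 1% | 32.2% / 19.8% | 12.4 | 1.92 |
| 4% / 4% | 33.6% / 19.2% | 14.4 | 2.13 |
| 1% / 4% | 34.65% / 19.2% | 15.45 | 2.23 |

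For the 4% / 1% row: 0.35 × 0.96 = 0.336; 0.20 × 0.99 = 0.198; OR = (0.336/0.664) / (0.198/0.802) = 2.05.

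**Effect on the test.** These checks use a Wald test of the log odds ratio without covariates and 160 dosed per arm.
- Borderline example: 46/160 against 32/160 gives p = 0.070. Removing 8 drug and 2 placebo failures gives 46/152 against 32/158, p = 0.043.
- No true difference, common rate 20% to 45%, and again 8 drug and 2 placebo failures removed: the simulated chance of a significant result in favour of drug rises from about 2.5% to between 3.7% and 5.2%.

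Both checks assume heavier loss on drug.

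**The case against.** **Few subjects are affected.** One result in any efficacy evaluation is enough for ITT. Protocol 13.3 asks discontinuers to return for the EOT assessments, and SAP Table 5 maps an early-termination diary to a scheduled week. A reader might infer that the earliest dropouts as a class disappear, but the documents do not support that. An early dropout who returns once for a diary review or an EOT scale stays in ITT and counts as a failure. This objection stands and limits the size.

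**The direction is unknown.** Protocol 10.1.1 discontinues subjects who cannot tolerate the assigned dose, so a reader might infer a bias toward drug. Those subjects are also asked back, and nothing in the documents shows that complete non-return differs by arm. With heavier loss on placebo, the planned analysis is conservative: it shows 2.15 where all dosed subjects give 2.23. This stands too.

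**A dosed set is also defined after randomization.** The first dose is taken at home and drug accountability starts at Week 1 (Protocol Table 2), so dosing may be unverifiable for someone who never returns. SAP 6.1.11.2 imputes only an unknown last-dose date. This stands and is the reason to prefer all randomized subjects.

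**The loss will be visible.** SAP 7.1.3 reports randomized, undosed, ITT and Safety counts by arm. That helps a reader, but it does not change the confirmatory p-value.

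**The 75% responder endpoint is not covered by this point.** A reader might extend the argument to it. SAP 7.2.6.2 defines that endpoint by the last assessed diary period and states no failure rule, so a subject without a post-baseline diary has no value and nothing is contradicted. It is also outside the alpha-controlled set.

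**Conclusion.** The inconsistency is clear on the text and is confined to 4-week cessation. Subjects whom the endpoint rule defines as failures are dropped from the denominator of a confirmatory analysis, and no analysis in the body of the SAP restores them.

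The effect is probably small. Under the assumed 35% and 20%, the odds ratio of 2.15 becomes 2.05 with 4% and 1% removed, and 1.92 with 8% and 1%. Equal losses barely move it. Only a result near the significance boundary, combined with unequal loss, would change its conclusion. All of these rates are assumptions, because the documents give neither cessation rates nor counts of subjects without efficacy results. The documents support neither a claim that the planned analysis is biased toward drug nor a claim that early dropouts in general are lost. The correction is still worth making, because it removes selection after randomization at almost no cost.

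**What to change.** Add one sentence to SAP 7.2.4.2: 4-week cessation is analysed by randomized arm in all randomized subjects, and a subject with no post-baseline diary is coded as no cessation. If all randomized is not acceptable, use at least all randomized and dosed subjects. Also report, by arm, how many subjects the ITT rule would have removed.

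Do not substitute the Safety population with its actual-treatment grouping. SAP 6.1.9 moves subjects randomized to 6 mg who stop on or before the Week 2 visit into the 4 mg group, which would misplace the very subjects at issue. Keep the current ITT set for the MMRM endpoints and leave the 75% responder analysis as it is.

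The cost is small. No new data or imputation model is needed, and both baseline covariates in the logistic model are recorded before randomization. Reported cessation rates will be slightly lower. The change should be made before database lock.

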10.1.1. Dose or Dosage for Study Drug

Subjects randomized to placebo will receive placebo for the duration of the treatment period.

Subjects randomized to 4 mg/day dasotraline will receive 4 mg/day for the duration of the treatment period.

Subjects randomized to 6 mg/day dasotraline will be dosed with 4 mg/day dasotraline for the first 2 weeks of the treatment period and will be increased to 6 mg/day at Week 2.

No other changes in dose are allowed during the study. Subjects who cannot tolerate the assigned dose at any time in the study will be discontinued.

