During the study and prior to database lock, the treatment assignments for all subjects are provided to the Bioanalytical Contract Research Organization (CRO) to facilitate plasma PK sample handling and analysis. No PK samples are analyzed for placebo subjects.

Protocol and IRT Amendment for Stratification Factor of Region

For this US study, there is no concern of ‘region’ difference for treatment effect. Sponsor’s initial intention of including stratification factor of region was to provide an optimization approach to ensure a balanced treatment assignment within each region. It should be noted that stratification by region was not implemented in study SEP360-221, which is also a US study with a similar study design.

The study team noticed on July 20, 2017 that the stratification by region was not implemented as planned, ie, the initiated sites in IRT were linked to incorrect regions (See [Section 6.1.5.1](#) for details). As of July 20, 2017, among 50 planned sites of this study, a total of 44 sites were screening subjects; and 137 subjects from 35 sites had already been randomized. Due to the ‘random’ nature of the incorrect assignment of region according to the root cause of this incident, the study team decided to remove stratification criteria related to ‘region’ to minimize the impact of this mistake. Stratification criteria were amended in study protocol V3.00 and randomization is to be balanced using only permuted blocks with baseline number of binge eating days per

321

week (3 – 4 binge eating days per week, > 4 binge eating days per week).

4. Changes in Planned Analyses

There is not any change made in this SAP from the analyses planned in the protocol.

5. Efficacy and Safety Variables

[Section 6.1.2](#) provides definitions of DB Baseline and Withdrawal Baseline. For the sake of simplicity, hereafter, Baseline and DB Baseline will be used in an interchangeable way.

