The Withdrawal Population: The withdrawal population includes all randomized subjects who receive at least one dose of study medication, and either discontinues the study drug during the treatment period before the Week 12 visit or completes the 12-week treatment period but do not enter the extension study (Study SEP360-322), and have at least 1 assessment after the last study drug for any safety or efficacy evaluation. The withdrawal population mainly is used to summarize the safety/efficacy assessments collected in the withdrawal period except of adverse event data.

The Modified Withdrawal Population: all subjects in the withdrawal population plus the subjects who do not enter the extension study and do not enter the withdrawal period, but the last study dose dates are at least 2 days earlier than the last study visit. The modified withdrawal population will be mainly used for adverse event that could be retrospectively collected.

Withdrawal analyses will be presented by planned treatment group for efficacy data and by actual treatment group for safety data.

Pharmacokinetics (PK) Population: The PK population is defined as all subjects who are randomized, receive at least 1 dose of study drug, and have any post-baseline plasma concentrations sample collection of dasotraline.

6.1.10 Stratification Factor ‘Baseline Number of Binge Days’ vs. Baseline Number of Binge Days Group

Group of Baseline number of binge days is defined as: Baseline number of binge days ≤ 4 , Baseline number of binge days >4 ; this group should be essentially equivalent to the stratification factor unless there is a subject stratified into the incorrect stratum. The stratification factor (ie, Baseline binge days category) will be consistently used in the statistical models, when applicable, for efficacy analysis as described in this document. Compared with the stratification factor, group of Baseline number of binge days will be used in the other scenarios, including the statistical models based analyses for safety variables.

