7.1.3 Disposition Information

Subject disposition for all randomized subjects will be summarized by treatment group using the following categories:

- Subjects who are randomized;
- Subjects who are randomized, but not dosed;
- Subjects in the ITT population;
- Subjects in the Safety population;
- Subjects in the PP population;
- Subjects in the ITT who complete the Week 12 visit;
- Subjects in the ITT who complete the Week 12 visit and enter into the open-label extension study;
- Subjects who discontinue during the DB period.

- Subjects in the withdrawal population;
- Subjects who complete the withdrawal period;
- Subjects who discontinue during the withdrawal period

For subjects who discontinue from the study after randomization, the corresponding reasons for discontinuation will be summarized for DB period and withdrawal period, respectively. For subjects who are excluded from the PP population, the corresponding reasons will be summarized by treatment.

For subjects who consented but were not randomized (eg, screen failures) the corresponding reasons for discontinuation will be summarized.

Kaplan-Meier plot of the time to early discontinuation in the DB period will be presented by treatment group. Subjects who complete 12-weeks DB treatment period will have their time to treatment discontinuation censored on the study day of end of the treatment period.

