7.4.7.1 Treatment Period

The number and percentage of subjects with following categories will be summarized by treatment for lifetime, baseline and any post-baseline in DB period, respectively.

- each type of suicidal ideation,
- any suicidal ideation,
- each type of suicidal behavior,
- any suicidal behavior,
- any having self-injurious behavior without suicidal intent,
- any suicidality

321

At any post-baseline visit in DB period, comparisons between each dasotraline group and placebo group for suicidality will be conducted using Fisher's exact test.

In addition, the number and percentage of subjects with following categories will also be summarized by treatment for any post-baseline in DB period.

- emergence of suicidal ideation,
- emergence of serious suicidal ideation,
- worsening of suicidal ideation,
- emergence of suicidal behavior,
- emergence of suicidality

Shift from baseline to any post-baseline in DB period in suicidal ideation score will be presented by treatment to show the percentage of subjects with values 0 ('No ideation present') to 5 ('Active ideation with plan and intent'). Descriptive statistics (N, mean, standard deviation, median, and range) will be reported for Ideation intensity total score at baseline, each scheduled post-baseline time point, and endpoint for observed value as well as change from baseline. Data collected on actual suicide attempts (lethality of actual attempts and potential lethality of attempts) will be presented in a data listing.

All summaries pertaining to the C-SSRS will be based on subjects in the safety population.

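### The SAP's safety grouping counts 6 mg-arm subjects who stop by the Week 2 visit as 4 mg, which moves early adverse-event discontinuations between doses and breaks the randomized comparison with placebo

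*SAP*

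**What the plan says.** Protocol 10.1.1 defines the 6 mg regimen with a lead-in: "Subjects randomized to 6 mg/day dasotraline will be dosed with 4 mg/day dasotraline for the first 2 weeks of the treatment period", followed by an increase to 6 mg/day at Week 2.

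Protocol 15.3 analyses the double-blind safety population by predominant treatment (the one with the longest exposure), but only "in the event that a subject receives a treatment other than the one to which he or she is randomized". It adds that the predominant treatment will generally equal the randomized one unless the subject takes incorrect medication for the whole study.

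SAP 6.1.9 replaces this with actual treatment and adds a specific rule "for subjects who are randomized to dasotraline 6 mg group and dosed with dasotraline 4 mg but never titrated to dasotraline 6 mg": if they were "early terminated on or prior to Week 2 visit), the actual dose will be dasotraline 4 mg". Every other subject randomized to 6 mg is set to 6 mg. For the withdrawal period, "Withdrawal analyses will be presented by planned treatment group for efficacy data and by actual treatment group for safety data".

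SAP Section 4 states: "There is not any change made in this SAP from the analyses planned in the protocol".

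**The concern.** A subject randomized to 6 mg who stops during the lead-in has received the assigned treatment up to that point. The SAP nevertheless moves that subject to another arm, and the trigger is early discontinuation, which intolerance can itself cause. Protocol 10.1.1 requires subjects who cannot tolerate the assigned dose to be discontinued.

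Once titration is a condition of membership, the 6 mg safety group has no discontinuations before titration by construction. The 4 mg group carries early stops from two arms, and placebo keeps its own. Neither dose is then compared with placebo as randomized in the outputs built on this population. These include adverse events leading to discontinuation (SAP 7.4.2), the laboratory rank ANCOVA and ANCOVA (7.4.3.1), the weight and BMI MMRM (7.4.5.1) and the C-SSRS analysis (7.4.7.1), where "comparisons between each dasotraline group and placebo group for suicidality will be conducted using" Fisher's exact test.

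This matters because comparing the doses is a stated purpose of the trial. Protocol 7.3.1 gives dose response as a reason for the fixed-dose design, and 7.3.2 frames the choice of 6 mg in terms of benefit and risk.

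**Working it through.** **Which principle does the SAP rule follow?**

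- *Randomized regimen:* no. Untitrated 6 mg-arm subjects followed their regimen and are moved.
- *Longest exposure:* not consistently. A 6 mg-arm subject who stops at Week 3 has had about 14 days on 4 mg and 7 on 6 mg, yet the SAP keeps that subject in 6 mg.
- *Dose at onset:* no. A Week 1 event on 4 mg counts under 6 mg if the subject continues past titration, and under 4 mg if the subject stops.

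What decides the group is whether the subject stopped by the Week 2 visit.

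**Inputs.** The planned arm size is 160, from 96 evaluable subjects per group and 40% dropout (Protocol 15.1): 96/(1 − 0.40) = 160, which reproduces the plan's figure. The documents give no rate of stopping by Week 2 and no adverse-event discontinuation rate, so all rates below are assumptions.

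**Formulas.** Let *e* be the proportion of an arm stopping by Week 2, *a* the proportion stopping by Week 2 because of an adverse event, and *t4* and *t6* the adverse-event discontinuation rates by randomized arm. Early experience is assumed equal in the two active arms because both take 4 mg. Then:

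- reported 4 mg = (t4 + a)/(1 + e)
- reported 6 mg = (t6 − a)/(1 − e)

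The arm size cancels; counts out of 160 are shown for transparency.

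| e | a (share of early stops, a/e) | By randomized arm, 4 mg vs 6 mg | Reported 4 mg | Reported 6 mg |
|---|---|---|---|---|
| 5% | 4 points (80%) | 10.0% vs 14.0% | (16 + 6.4)/168 = 13.3% | (22.4 − 6.4)/152 = 10.5% |
| 3% | 2 points (67%) | 8.0% vs 12.0% | (12.8 + 3.2)/164.8 = 9.7% | (19.2 − 3.2)/155.2 = 10.3% |
| 2% | 1 point (50%) | 10.0% vs 14.0% | (16 + 1.6)/163.2 = 10.8% | (22.4 − 1.6)/156.8 = 13.3% |
| 5% | 2 points (40%) | 10.0% vs 14.0% | (16 + 3.2)/168 = 11.4% | (22.4 − 3.2)/152 = 12.6% |
| 5% | 1 point (20%) | 10.0% vs 14.0% | (16 + 1.6)/168 = 10.5% | (22.4 − 1.6)/152 = 13.7% |
| 5% | 0.5 points (10%) | 10.0% vs 14.0% | (16 + 0.8)/168 = 10.0% | (22.4 − 0.8)/152 = 14.2% |

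**Direction.** The 4 mg rate rises when a/e > t4, and the 6 mg rate falls when a/e > t6. In the last row a/e equals t4 and is below t6, so 4 mg is unchanged and 6 mg rises slightly.

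**Reversal of the dose order.** This needs a > [(t6 − t4) + e(t6 + t4)]/2. With 10% vs 14% and e = 5%, that is (0.04 + 0.05 × 0.24)/2 = 2.6 points. Only the first row reverses.

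**Extreme case.** Suppose all 8 early stops per arm are due to adverse events and each arm has 8 later ones. The randomized rates are equal, at 16/160 = 10.0%. Reported rates are 24/168 = 14.3% for 4 mg and 8/152 = 5.3% for 6 mg.

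**Against placebo.** With an assumed placebo rate of 4% and the first row, the 4 mg excess goes from 6.0 to 9.3 points and the 6 mg excess from 10.0 to 6.5.

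**Overall adverse-event incidence.** With 60% (96/160) in both arms and 8 subjects moved, *k* of whom had an event, the 4 mg rate is (96 + k)/168 and the 6 mg rate (96 − k)/152:

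- k = 8: 61.9% vs 57.9%
- k = 4: 59.5% vs 60.5%
- k = 0: 57.1% vs 63.2%

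The sign is not fixed for this output.

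**The case against.** - **The protocol also groups by treatment received.** Section 15.3 names the treatments by dose, and an untitrated subject was exposed only to 4 mg/day, so the SAP could be read as filling in that rule. However, 15.3 applies it only when a treatment other than the randomized one is taken, and its last sentence refers to incorrect medication throughout the study. The SAP rule is also not a longest-exposure rule. At the least, the two texts need reconciling.
- **The information is partly available elsewhere.** SAP 7.1.3 says "Subject disposition for all randomized subjects will be summarized by treatment group", with reasons for discontinuation and a Kaplan-Meier plot, and the dropout profiles in 7.2.3.2.6 also cover these subjects. This stands as a limit if treatment group means randomized arm in those sections. It does not supply adverse-event incidence by randomized arm.
- **Safety is descriptive.** SAP 7.4.1 says so, and no safety test is in the alpha-controlled family. That removes any type I error issue but not the bias in the displayed rates, and model-based and Fisher comparisons are planned all the same.
- **The size is unknown.** This stands. If few early stops are due to adverse events, the effect is close to nil.
- **Grouping by dose taken avoids charging 6 mg with events in people who never took it.** This is a fair aim, but a dose-at-onset table meets it without regrouping on dropout. For withdrawal-period outputs the objection is stronger, since a subject who stopped on 4 mg would be shown as withdrawing from the 6 mg regimen. That part of the remedy is debatable.

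**Conclusion.** The concern holds. The SAP rule makes safety-group membership depend on early stopping, departs from the natural reading of Protocol 15.3, and is not declared in SAP Section 4. None of this rests on assumed figures.

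The adverse-event discontinuation rate is biased up for 4 mg and down for 6 mg whenever the adverse-event share of early stops exceeds each arm's own rate. That is the likely situation in a trial that discontinues subjects for intolerance, but it is a judgement, not a figure in the documents. Under the assumptions tried, the effect runs from almost none to a reversed dose order. For overall adverse-event incidence and other safety outputs, direction and size depend on the data of the subjects moved. ITT and per-protocol efficacy analyses are by randomized arm and are unaffected. This should be fixed before unblinding.

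**What to change.** Group the double-blind safety population by assigned regimen: placebo; 4 mg; 4 mg for two weeks then 6 mg. Reassign only subjects who took the wrong study drug, as Protocol 15.3 provides. Apply the same grouping to withdrawal-period safety outputs or, if dose at stopping is preferred there, justify it explicitly. If attribution to dose is wanted, add a supplementary table of events by dose at onset with person-time denominators. State that treatment group in SAP 7.1.3 means randomized arm.

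If the current rule is kept, list it in SAP Section 4 as a change from the protocol and show adverse-event discontinuations by randomized arm beside the actual-treatment table.

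The cost is SAP wording and one derived treatment variable, plus the supplementary table if it is added. The 6 mg discontinuation figures may look less favourable, and without that table events in subjects never exposed to 6 mg would appear only under the 6 mg regimen.
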